4.1 Objectives

Primary objective

To confirm the superiority of liraglutide at the maximum tolerated dose (0.6 mg, 1.2 mg or 1.8 mg) versus placebo when added to metformin with or without basal insulin treatment in controlling glycaemia in children and adolescents (ages 10–17 years) with type 2 diabetes.

Secondary objectives

To assess and compare the effect of liraglutide versus placebo in combination with metformin with or without basal insulin treatment on:

- Parameters of glycaemic control
- Parameters of beta-cell function
- Parameters of body composition
- Vital signs
- Growth velocity (if subject is still growing)
- Safety and tolerability
- Growth and pubertal development at 1 and 2 year follow up after trial drug cessation at week 52

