5.3.2 Liraglutide

Liraglutide and liraglutide placebo are administered once daily by s.c. injections, either in the abdomen, thigh or upper arm. The injection site does not have to be consistent throughout the trial. Injections can be done at any time of the day and irrespective of meals. It is recommended that the time of injection is consistent throughout the trial. Subjects will be instructed to perform an air shot before the first use of a new prefilled pen. Liraglutide vehicle will be used as placebo. In this trial liraglutide and liraglutide placebo are characterised as investigational medicinal products (IMPs).

After randomisation, liraglutide or liraglutide placebo will be escalated weekly starting at 0.6 mg and increasing with 0.6 mg increments over 2-3 weeks. Dose escalation will be based on tolerability (dose should not be increased in case severe intolerability is experienced, as judged by the investigator) and the following: the average of 3 measurements of FPG > 6.1 mmol/L (110 mg/dL) performed by the subject at home on the three consecutive days preceding the dose escalation visit (Visits 8, 9 and 10, please see [Figure 5-2](#)). After end of the liraglutide dose escalation period no further dose escalations must be performed.

Subjects treated with basal insulin experiencing hypoglycaemia should reduce the dose of basal insulin (if needed to 0 units) before the dose of liraglutide/liraglutide placebo is decreased.

[figure not shown]

Figure 5–2 Dose escalation of liraglutide

During the blinded period, escalation at each YES/NO decision point should be determined by whether the subjects average FPG is > 6.1 mmol/L (110 mg/dL).

In the event that a subject experiences severe intolerance or recurrent hypoglycaemia as judged by the investigator (such as ≥ 3 unexplained minor hypoglycaemic events or 1 severe unexplained hypoglycaemic event in a week) the dose will be lowered to the next decreased level (from 1.8 mg to 1.2 mg or from 1.2 mg to 0.6 mg). The reason for down escalation of liraglutide must be documented in the subject's medical record and transferred to the eCRF.

If a subject treated with 0.6 mg experiences severe intolerance or recurrent hypoglycaemia as judged by the investigator (such as ≥ 3 unexplained minor hypoglycaemic events or 1 unexplained severe hypoglycaemic event in a week) the subject must be withdrawn from the trial.

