5.3.5 Rescue treatment

Subjects experiencing confirmed hyperglycaemia as per rescue criterion no. 1 (see section [6.5](#)), will be offered rescue treatment. Subjects on rescue treatment will remain in the trial.

Rescue treatment will be as follows:

- Subjects treated with metformin and liraglutide/liraglutide placebo may have basal insulin added. The start dose and basal insulin titration will be at the discretion of the investigator. If subjects continue to experience confirmed hyperglycaemia as

per rescue criterion no. 1 a rapid acting insulin may be added and titrated at the discretion of the investigator.

- Subjects treated with metformin, basal insulin and liraglutide/liraglutide placebo may have the basal insulin dose increased; the dose and basal insulin titration will be at the discretion of the investigator. If subjects continue to experience confirmed hyperglycaemia as per rescue criterion no 1 a rapid acting insulin may be added and titrated at the discretion of the investigator.

If hyperglycaemia is persistent and meets the withdrawal criterion no. 5 despite rescue treatment having been initiated, the subject must be withdrawn from the trial (see section [6.5](#))

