8.6.3 Blood samples

Blood samples will be drawn at site at the specified time-points (section [2](#)) and analysed at the central laboratory to determine levels of the following efficacy laboratory parameters:

- Glucose metabolism
 - HbA_{1c}
 - FPG
 - Fasting C-peptide
 - Fasting insulin
 - Fasting pro-insulin
 - Fasting glucagon

- Lipids
 - Cholesterol
 - LDL cholesterol
 - HDL cholesterol
 - VLDL cholesterol
 - Triglycerides
 - Free fatty acids

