Laboratory data from central laboratories will be transferred electronically from the laboratory performing the analyses. In cases where laboratory data are transferred via non-secure electronic networks, data will be encrypted during transfer. The laboratory will provide all laboratory reports to the investigator for storage at the trial site.

The subject and any biological material obtained from the subject will be identified by subject ID and trial identification number. Appropriate measures such as encryption or leaving out certain identifiers will be enforced to protect the identity of subjects in all presentations and publications as required by local, regional and national requirements.

16 Computerised systems

Novo Nordisk will capture and process clinical data using computerised systems that are described in Novo Nordisk Standard Operating Procedures (SOPs) and IT architecture documentation. The use and control of these systems are documented.

Investigators working on the trial may use their own electronic systems to capture source data. Novo Nordisk will collect information on the practical use of these systems within the conduct of this clinical trial.

17 Statistical considerations

General considerations

Novo Nordisk will be responsible for the statistical analysis and reporting. Analysis and reporting will be based on pooled data from all sites.

The statistical analyses will be performed with a significance level of 5% (two-sided tests).

For all endpoints analysed statistically, estimated mean treatment differences will be presented together with two-sided 95% confidence intervals and p-values.

Handling of missing data

If an assessment has been made both at screening and randomisation, and if not otherwise specified, the value from the randomisation visit will be used as the baseline value. If the value measured at the randomisation visit is missing and the assessment also has been made at screening, then the screening value will be used as the baseline value.

For efficacy variables missing values will be imputed as described in section [17.3](#) and [17.4](#).

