17.1 Sample size calculation

The sample size has been determined in order to demonstrate superiority of liraglutide in combination with metformin with or without basal insulin treatment vs. liraglutide placebo with metformin with or without basal insulin treatment, with regards to change in HbA_{1C} from baseline after 26 weeks, using a significance level of 5% and a two-sided test.

The sample size is based on calculations for the primary endpoint alone. Assumptions for the sample size calculations are as follows:

Change in HbA_{1c}: a mean difference of 0.9% of liraglutide in combination with metformin with or without basal insulin treatment vs. liraglutide placebo with metformin with or without basal insulin treatment; Standard deviation (SD) =1.2%. The change in mean difference was chosen based on the effect of liraglutide vs. placebo observed in the adult population (LEAD 1, 2, 4 and 5 trials)¹⁵ and a paediatric PK/PD trial which included HbA_{1c} after 5 weeks of treatment as an exploratory endpoint (NN2211-1800)³⁶.

The chosen withdrawal rates (see table 17.1) are based on the withdrawal rates seen in the LEAD 2 trial¹⁵ where the withdrawal rate was approximately 40% for the placebo group and approximately 20% for the active groups. A slightly higher withdrawal rate is assumed as the trial is performed in a paediatric population. Therefore, the withdrawal rate for the active group is assumed to be 22%. The primary analysis will impute measurements for withdrawn placebo subjects based on placebo completers, and thus the sample size is not adjusted for placebo withdrawal rate.

Based on these assumptions, the sample size is set to 47 in each of the liraglutide and liraglutide placebo arms for the full analysis set (FAS) in order to achieve 80% power see [Table 17-1](#).

Assuming a screening failure rate of 65%, 269 subjects will need to be screened.

Table 17-1 Total sample size for a 1:1 randomisation

		Difference to detect in subjects with week 26 data				
Withdrawal rate		0.6%	0.7%	0.8%	0.9%	1.0%
20	Adjusted difference	0.48%	0.56%	0.64%	0.72%	0.80%
	Sample size	200	148	114	90	74
22	Adjusted difference	0.47%	0.55%	0.62%	0.70%	0.78%
	Sample size	210	154	120	94	78
25	Adjusted difference	0.45%	0.53%	0.60%	0.68%	0.75%
	Sample size	226	166	128	102	84

Power: 80%

Standard deviation of change in HbA_{1c} (%) from baseline at week 26 assumed to be 1.2%

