3.6 Secondary endpoints

3.6.1 Confirmatory secondary endpoints

All confirmatory secondary endpoints will be presented and analysed using FAS, unless otherwise specified.

The primary analysis for the confirmatory secondary endpoints is the pattern mixture model using multiple imputation and using all available data, including data collected after treatment discontinuation and initiation of rescue medication. The model is described in detail in the primary analysis for the primary endpoint, except that the baseline value of the analysed endpoint will be included instead of the baseline HbA_{1c} . value For the dichotomous endpoint (HbA_{1c} <7.0%), a

Liraglutide Trial ID: NN2211-3659	CONFIDENTIAL	Date: Version:	2.0	Novo Nordisk
Statistical Analysis Plan EurdraCT No.: 2011-002605-29		Status: Page:	Final 16 of 25	ı

logistic regression model will be used with missing values imputed from the pattern mixture model of change from baseline in HbA_{1c}

In addition, the confirmatory secondary endpoints will be analysed by an MMRM model using all data points for all visits, but excluding data collected after treatment discontinuation or initiation of rescue medication. Fixed factors in the model are treatment and stratification groups (gender*age group), with baseline value of the analysed endpoint included as covariate., Both fixed factors and the covariate will be nested within visit (sensitivity analysis no. 4 for the primary endpoint). For measurements within a subject an unstructured covariance will be used. For the dichotomous endpoint (HbA_{1c}<7.0%), a logistic regression model will be used with missing values imputed from the corresponding MMRM model of change from baseline in HbA_{1c}.

The continues confirmatory endpoints will be presented as described for the primary analysis.

Change from baseline in FPG after 26 weeks of treatment

The change from baseline in FPG after 26 weeks of treatment will be analysed with the same method as the primary efficacy endpoint (as described above). Baseline FPG will be included in the analyses instead of baseline HbA_{1c} .

$HbA_{1c} < 7.0\%$ after 26 weeks of treatment (yes/no)

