 - post-prandial increments after breakfast, lunch and dinner (from before meal to 90 min after breakfast, lunch and dinner)
 - mean post-prandial increment for all meals (breakfast, lunch, and dinner)
- Fasting insulin, fasting pro-insulin, pro-insulin to insulin ratio, fasting glucagon, fasting C-peptide, and homeostasis model assessment (HOMA-B and HOMA-IR). The values will be logarithmically transformed before analysis, and the actual values will be modelled instead of change from baseline.
- Fasting lipid profile (total cholesterol, LDL cholesterol, VLDL cholesterol, HDL cholesterol, triglycerides and free fatty acids. The values will be logarithmically transformed before analysis, and the actual values will be modelled instead of change from baseline.
- Body weight
- Waist circumference
- BMI
- BMI SDS at 52 weeks
- BMI percentile (age and gender adjusted)
- Systolic and diastolic blood pressure

Throughout the trial:

• Basal insulin dose

For calculation of BMI SDS please refer to section 3.6.1 above.

BMI percentile (age and gender adjusted) is the result of the cumulative normal distribution function based on the respective Z-value (SDS value).

Liraglutide
Trial ID: NN2211-3659
Statistical Analysis Plan
EurdraCT No.: 2011-002605-29

Date: 25 June 2018 Version: 2.0
Status: Final
Page: 19 of 25

The continuous endpoints described above will be analysed with a similar method as for the primary endpoint (detailed above), except for change in basal insulin dose that will only be presented by descriptive statistics. The BMI percentile will also only be summarised (descriptive statistics) as it is uniquely determined from the BMI SDS. The post prandial increments after breakfast, lunch, and dinner will also only be presented by descriptive statistics, whereas the mean post-prandial increment will be analysed as the other endpoints.

If data has been log transformed, the ratio to baseline and treatment ratio will be considered instead of the change from baseline and treatment difference.

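### Insulin-based secondary measures (fasting insulin, pro-insulin:insulin ratio, HOMA) are analysed in all subjects without separating injected from endogenous insulin, so the arm contrast can be biased

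*SAP*

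**What the plan says.** **Objective and measures.** Protocol 4.1 lists "Parameters of beta-cell function" among the secondary objectives. It does not say which measures answer it. SAP 3.6.2 names "Fasting insulin, fasting pro-insulin, pro-insulin to insulin ratio, fasting glucagon, fasting C-peptide, and homeostasis model assessment (HOMA-B and HOMA-IR") as supportive endpoints at weeks 26 and 52, log-transformed and analysed in the FAS. SAP 2.2.2 marks them for public disclosure, and SAP 3.3 gives every statistically analysed endpoint a confidence interval and p-value.

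**Analysis.** By SAP 3.6.1, which 3.6.2 adopts, the lead model works "using all available data, including data collected after treatment discontinuation and initiation of rescue medication". An additional MMRM drops data after rescue or treatment discontinuation. The ANCOVA in SAP 3.5 has terms for treatment, sex-by-age stratum and baseline value, and no insulin term. Baseline insulin use enters the imputation model only. The insulin interaction analysis (SAP 3.7) covers HbA1c only.

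**Insulin in the trial.** Protocol 5.3.3 lets subjects enter on intermediate-acting human insulin or an intermediate- or long-acting analogue. In both arms it cuts the dose by 20% at randomisation and later allows glucose-guided increases up to the screening dose. Under Protocol 5.3.2, insulin-treated subjects with hypoglycaemia "should reduce the dose of basal insulin (if needed to 0 units) before the dose of liraglutide/liraglutide placebo is decreased". Under Protocol 5.3.5, "Subjects treated with metformin and liraglutide/liraglutide placebo may have basal insulin added" as rescue; those already on basal insulin may have it increased, and rapid-acting insulin may follow.

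**Sampling.** Protocol 8.6.3 also collects "Fasting C-peptide" and FPG. Protocol 8.4 leaves assay methods to the laboratory manual. Neither document gives a HOMA formula.

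**The concern.** Fasting insulin, the pro-insulin:insulin ratio and an insulin-based HOMA are informative about a subject's own secretion or resistance only if the measured insulin is the subject's own. Here some subjects inject insulin from the start and others begin it as rescue. Human insulin is the same molecule as the endogenous hormone. How far an analogue is counted depends on the assay. The fast in Protocol 8.1.5 withholds diabetes medication for at least eight hours, but does not require that a basal dose given before then has cleared.

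If injected insulin ends up higher on placebo, placebo fasting insulin rises and its pro-insulin:insulin ratio falls with no difference in endogenous secretion. A published treatment ratio, with its p-value, could then be read as an effect of liraglutide on the beta cell or on insulin resistance when it reflects who was injecting insulin.

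**Working it through.** **1. The plan's own figure.** The only sample size is for HbA1c, set "in order to achieve 80% power" (Protocol 17.1). The diluted difference is 0.9 × (1 − 0.22) = 0.702, with SD 1.2 and two-sided 5%. The normal approximation gives 2 × (1.96 + 0.842)² × 1.2² / 0.702² = 45.9, so 46 per arm. The exact t calculation gives 47 per arm, 94 in total, as stated. The plan gives no figure for the insulin-based endpoints, and N is not affected by this point.

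**2. Can injected insulin differ by arm?**
- Use at entry: balanced in expectation by randomisation.
- Rescue: triggered by glucose in both arms, with a tighter limit after week 14 (Protocol 6.5). Protocol 3.1.5 anticipates a need for rescue on placebo, but in explaining the unblinding after week 26, so it bears mainly on week 52.
- Basal dose: the rules are the same in both arms but respond to glucose. Protocol 3.1.3 reports that in adults the combination seemed associated with less need for insulin.

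A difference is therefore plausible, but the documents do not quantify it.

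**3. Rescue route (lead analysis).** Let *f* be the factor by which injected insulin raises measured fasting insulin, and *d* the excess share of subjects on insulin in the placebo arm. On the log scale with no true effect, the liraglutide/placebo ratio is *f*^(−*d*). Both inputs are assumptions, as is detection of the insulin by the assay.

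| *f* | *d* = 10 points | 20 points | 30 points |
|---|---|---|---|
| 1.25 | 0.978 | 0.956 | 0.935 |
| 1.5 | 0.960 | 0.922 | 0.885 |
| 2 | 0.933 | 0.871 | 0.812 |
| 3 | 0.896 | 0.803 | 0.719 |

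With pro-insulin unchanged, the pro-insulin:insulin ratio moves by the inverse: 2^0.2 = 1.15 at *f* = 2 and 20 points. Insulin-based HOMA-B and HOMA-IR would move by the fasting-insulin factor only at fixed glucose. Rescue is given to lower glucose, so the two need not shift equally.

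**4. Chance of a misleading significant result.** Take *f* = 2, *d* = 20 points, so |ln 0.871| = 0.139, with 47 per arm all observed and an assumed log-SD of 0.5 to 0.7.
- SD 0.5: standard error 0.5 × √(2/47) = 0.103, z = 1.34, probability Φ(1.34 − 1.96) = 27%.
- SD 0.7: standard error 0.144, z = 0.96, probability 16%.

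The nominal figure in that direction is 2.5%. Missing data and imputation would alter these values.

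**5. Entry route (what the MMRM leaves).** Let *p* be the share on basal insulin at entry and *e* the injected fraction of their measured insulin. If liraglutide subjects stay at 80% of their dose and placebo subjects return to 100%, the ratio is (1 − 0.2*e*)^*p*.
- *p* = 10%, *e* = 0.25: 0.95^0.10 = 0.995.
- *p* = 31.1%, *e* = 0.75: 0.85^0.311 = 0.95.

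The 31.1% is an external cohort's insulin use (Protocol 5.4), taken as an upper scenario. Only if every insulin user on liraglutide came down to 0 units, with placebo at full dose, would the ratio be (1 − *e*)^*p*, running from 0.97 to 0.65 over the same ranges.

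**The case against.** **The bias is not demonstrated.** A reader might infer that injected insulin is certainly counted as beta-cell output. The documents do not support that: they give neither the HOMA formula nor the assay's specificity. If HOMA is already based on C-peptide, or the assay misses the analogues used, the problem shrinks. This stands; the claim is conditional.

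**The imbalance is not stated for week 26.** It is tempting to read Protocol 3.1.5 as forecasting more placebo rescue at week 26, and Protocol 5.3.2 as lowering insulin only on liraglutide. The first refers to the period after week 26 and the second covers both arms. This stands too, though glucose-driven rules can still produce different insulin exposure.

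**The MMRM already handles rescue.** It does, and the rescue route gives the 0.87 illustration. But it is the additional analysis, it keeps subjects on basal insulin from entry, and it rests on a missing-at-random assumption.

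**Keeping post-rescue data follows the treatment-policy estimand (SAP 4.1).** That is coherent for HbA1c. For an index meant to reflect endogenous secretion, the rescue drug may enter the measurement itself, so the estimand does not settle what is being measured.

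**The objective survives.** Fasting C-peptide and pro-insulin are analysed by the same models and do not measure injected insulin directly, and HOMA-IR is an index of resistance rather than secretion. This stands: the objective does not go unanswered.

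**Conclusion.** The point holds in conditional form. As written, the plan can give a misleading treatment ratio for fasting insulin, the pro-insulin:insulin ratio and any insulin-based HOMA, because nothing separates injected from endogenous insulin and exposure after randomisation can differ by arm. In the lead analysis, a doubling of measured insulin and a 20-point excess on placebo give about 0.87 for fasting insulin and 1.15 for the pro-insulin:insulin ratio under a null effect. Across the rescue scenarios the fasting-insulin ratio runs from 0.98 to 0.72. In the MMRM the remaining bias is probably smaller (0.995 to 0.95 unless liraglutide subjects largely stop insulin).

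The fold rise, the excess insulin use, the injected fraction and the log-SD are all assumptions, so the actual size, or whether any bias occurs, cannot be fixed from the documents. A reader should not infer that the contrast is known to be biased, that HOMA-B and HOMA-IR move equally, or that the beta-cell objective is lost. These endpoints are supportive and outside the hierarchy; the primary and confirmatory results are unaffected.

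**What to change.** In SAP 3.6.2:

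1. Name fasting C-peptide as the lead beta-cell measure.
2. Derive HOMA-B and HOMA-IR from fasting C-peptide and FPG, and state the formula.
3. Present fasting insulin, the pro-insulin:insulin ratio and any insulin-based HOMA for subjects without basal insulin at baseline, using the flag already defined in SAP 3.3, and label them as such.
4. For post-rescue samples in that subgroup, use the MMRM handling already planned. State that it conditions on a post-randomisation event and assumes missing at random.

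Simply setting aside every sample after insulin start, without step 4's caveat, would not be a clean cure: the placebo subjects left would be those who did not need rescue, which exchanges one bias for another. The baseline subgroup avoids this for insulin use at entry because it is defined before randomised treatment.

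The cost is SAP wording and a derived variable for each index. C-peptide, FPG and baseline insulin dose are already collected. The downside is a smaller sample for the insulin-based supportive measures.

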3.6.3 Safety endpoints

All safety endpoints will be presented using the safety analysis set. Unless otherwise specified safety endpoints will be presented only by descriptive statistics.

Change from baseline at 26 and 52 weeks of treatment unless otherwise stated

- Clinical evaluations (physical examination including fundoscopy [fundoscopy at 26 and 52 weeks])
- ECG with rhythm strip (at 26 and 52 weeks)
- Laboratory tests:
 - Haematology (haemoglobin, haematocrit, thrombocytes, erythrocytes, leucocytes and differential count (eosinophils, neutrophils, basophils, lymphocytes and monocytes)
 Biochemistry (creatinine, creatine kinase, urea, albumin, bilirubin (total), ALAT, ASAT, sodium, potassium, alkaline phosphatase, calcium, calcium (albumin corrected), amylase and lipase)
 - Hormones (calcitonin, prolactin, FSH, estradiol, LH, testosterone, DHEAS, CEA and TSH, IGF-1, IGFBP-3
 - First morning urinalysis (Micro albumin, creatinine, albumin:creatinine ratio calculated, protein, ketone, glucose, pH)
 - o Biochemical parameters of bone metabolism: Alkaline Phosphatase, NTX, CPX, P1NP
 - o Formation of anti-liraglutide antibodies (at 26 and 53 weeks)
- Pulse
- Pubertal assessment/ progression (Tanner staging), DHEAS, LH, FSH, estradiol in females and testosterone in males
- Height SDS versus baseline at 26 and 52 weeks
- Bone age assessment (x-ray of left hand and wrist) at 52 weeks

In addition the following will be assessed at 26, and 52 weeks:

 Assessment of compliance (questioning of subjects and subjects legally acceptable representative)

Liraglutide		Date:	25 June 2018	Novo Nordisk
Trial ID: NN2211-3659	CONFIDENTIAL	Version:	2.0	
Statistical Analysis Plan		Status:	Final	
EurdraCT No.: 2011-002605-29		Page:	20 of 25	

• Growth (height) velocity in cm/year and height (growth) velocity SDS (if subject is still growing). A growth (height) velocity < 1.0 cm/year is defined as no longer growing.

Collected throughout the trial:

- Hypoglycaemic episodes (see details below)
- AEs and serious adverse events (SAEs) (see details below)

Pulse

Pulse will be analysed with a similar method as for the primary analysis for the primary endpoint (as described for the secondary confirmatory and supportive efficacy endpoints).

Height SDS

Height SDS will be calculated using the same formula as described for BMI SDS (see section 3.6.1) The values for M, S and L are downloaded from

http://www.who.int/growthref/hfa_boys_perc_WHO2007_exp.txt and http://www.who.int/growthref/hfa_girls_perc_WHO2007_exp.txt on 2nd February, 2018)

Height velocity

Growth (height) velocity is the change in height per year and is measured in cm/year (height velocity is the same as growth velocity).

The height velocity is calculated as the difference between current height and baseline divided by time duration in days between those measurement time points and multiplied by 365 days.

Height velocity SDS

Height velocity SDS will be calculated using the same formula as described for BMI SDS (see section 3.6.1) The reference values for M, S and L are downloaded from https://academic.oup.com/jcem/article/99/6/2104/2537746. Height velocity SDS at week 26 will only be used to find extreme outliers as it is not recommended to calculate this value based on height change over less than one year.

Hypoglycaemic episodes

Hypoglycaemic episodes are recorded by subjects in their trial diaries throughout the trial. The information collected includes plasma glucose (PG) before treating the episode and whether the subject was able to treat him/herself. This information is used by Novo Nordisk to classify an episode according to the ADA definition (severe, documented symptomatic, asymptomatic, probable symptomatic and relative) and the additional minor category as defined by Novo Nordisk (also named as BG confirmed). A hypoglycaemic episode is defined as treatment emergent if the onset of the episode is on or after the first day of exposure to randomised treatment and no later than one day after the last day on randomised treatment. All hypoglycaemic episodes will be summarised by treatment and severity.

Nocturnal hypoglycaemic episodes, defined as episodes with time of onset between 00:01 and 05:59, will also be summarised by severity. In addition the hypoglycaemic episodes will be

Liraglutide		Date:	25 June 2018	Novo Nordisk
Trial ID: NN2211-3659	CONFIDENTIAL	Version:	2.0	
Statistical Analysis Plan		Status:	Final	
EurdraCT No.: 2011-002605-29		Page:	21 of 25	

summarised by events occurring at periods in the trial when the subjects are on basal insulin and/or bolus insulin, and at periods without insulin.

The hypoglycaemic episodes will be summarised for the blinded period of the trial (up to week 26) and for the total exposure period.

Adverse events

All AEs will be coded using the most recent version of the Medical Dictionary for Regulatory Activities (MedDRA). A treatment emergent adverse event (TEAE) is defined as an event that has onset date (or increase in severity) on or after the first day of exposure to randomised treatment and no later than seven days after the last day of randomised treatment. In the open period of the trial the randomised treatment for placebo is metformin alone.

The TEAEs will be summarised by treatment for all TEAEs by system organ class, preferred term, seriousness, severity, outcome and relation to trial product. TEAEs are summarised descriptively in terms of the number of subjects with at least one event (N), the percentage of subjects with at least one event (%), the number of events (E) and the event rate per 1000 years (R).

The most frequent TEAEs will be defined as preferred terms that are experienced by at least 5% of the subjects in any of the treatment arms. The most frequent TEAEs will be summarised and presented in a plot with number of subjects with an event and rate of events (number per 1000 years of exposure).

The TEAEs will be summarised for the blinded period of the trial (up to week 26) and for the total exposure period.

Non-treatment emergent AEs will be presented in listings.

Medical events of special interest (MESI) will be summarised separately.

MedDRA search terms have been defined to find AEs of special interest in the following categories: Cardiac events, Pancreatitis, Medication error, Neoplasm, Thyroid disease, Altered renal function, Injection site reactions, Overdose, Gallstone, Cardiac arrhythmia, Hyperglycaemia, Allergic reaction, Elevated amylase, Elevated calcitonin, Suspected transmission of infectious agents, Rare adverse events, Depression adverse events, Device issue events and Immune adverse events. These MedDRA search terms are defined prior to DBL (5). The AEs of special interest will be listed by category.

3.6.4 Safety follow-up at 1 and 2 years after trial drug cessation at week 52 (only applicable for subjects on active liraglutide treatment for more than 3 months)

- AEs and SAEs
- Growth (height) velocity in cm/year (if subject is still growing)

Liraglutide
Trial ID: NN2211-3659
Statistical Analysis Plan
EurdraCT No.: 2011-002605-29

Date: 25 June 2018 Version: 2.0
Status: Final
Page: 22 of 25

• Height velocity SDS (height velocity is the same as growth velocity) (if subject is still growing)

Change in:

- Height SDS
- Pubertal assessment/progression by Tanner staging
- Bone age assessment (x-ray of left hand and wrist)

For calculation of height SDS please refer to section 3.6.2.

